## 5.1 Agent Administration

Treatment will be routinely administered on an outpatient basis. rhIL-15 will be given through SC injections, and nivolumab and ipilimumab will be administered through IV infusion (nivolumab over 30 minutes and ipilimumab over 90 minutes). IL-15 will be prepared in D5W/0.1% HSA or normal saline at no less than 100 mcg/mL in sterile borosilicate vials prior to being loaded in the syringes. Nivolumab can be infused undiluted (10 mg/mL) or diluted with 0.9% Sodium Chloride Injection, USP or 5% Dextrose, USP to concentrations no less than 0.35

mg/mL. Ipilimumab is given undiluted or further diluted in 0.9% NaCl Injection, USP or 5% Dextrose Injection, USP in concentrations between 1 mg/mL and 4 mg/mL. See [Section 8](#) for more details about study agent administration.

Administration of study drugs will be performed in a setting with emergency management capabilities and staff who are trained to monitor for and respond to medical emergencies. Patients will be informed about the possibility of delayed post-infusion symptoms and instructed to contact their study physician if they develop such symptoms.

Reported adverse events and potential risks are described in [Section 7](#). Patients will be encouraged to report any and all adverse events, given the high likelihood of toxicities with the triplet combination therapy. No investigational or commercial agents or therapies other than those described below may be administered with the intent to treat the patient's malignancy.

### 5.1.1 Lead-In Doublets

The first 4-6 patients enrolling in the study will be placed into one of two lead-in doublets (nonrandomized; investigator's choice): rhIL-15 + nivolumab (2-3 patients) or rhIL-15 + ipilimumab (2-3 patients). rhIL-15 will be given on days 1-8 and 22-29 in combination with either nivolumab (days 8, 22, and 36) or ipilimumab (day 8). Doses are shown below.

	Dose
rhIL-15 (first 4 cycles only)	0.5 mcg/kg/day SC
Nivolumab	240 mg IV (over 30 min)
Number of pts	3

**OR**

	Dose
rhIL-15 (first 4 cycles only)	0.5 mcg/kg/day SC
Ipilimumab	1 mg/kg IV (over 90 min)
Number of pts	3

Doublets are for evaluation of safety only, and assessment of toxicities will take place during and after the first cycle. Each doublet will enroll up to 3 patients; a doublet will be considered as clearing toxicity once at least 2 patients enrolled on the doublet tolerate the treatment for 6 weeks (i.e., do not experience a DLT). If 1 patient on the doublet experiences a DLT, 1 or 2 more patients will be enrolled for a total of 3; if 2 of the 3 patients experience a DLT, enrollment into the triplet cohort will not occur, and the study will be halted and reevaluated.

rhIL-15 administration will be limited to the first 4 cycles of treatment. After completing 4 cycles, patients in a doublet cohort may continue onto single checkpoint inhibitor therapy for cycles 5 and onwards; they may not continue receiving rhIL-15 or enter the triplet cohort.

After completion of the doublet phase, the trial will be halted and a safety analysis will be submitted to the IRB. The triplet phase will not be opened to enrollment until a review of the safety and efficacy data is conducted.

### 5.1.2 Triplet Cohort Dose Levels

New patients will be enrolled onto the triplet dose escalation cohort only after toxicity is cleared in both lead-in doublets and a safety analysis is reviewed by the IRB (see [Section 5.1.1](#)).

*As of Amendment C (10/3/18), toxicity has been cleared in both lead-in doublets. 3 patients were enrolled on Doublet A (rhIL-15 + nivolumab) and 2 patients were enrolled on Doublet B (rhIL-15 + ipilimumab); none of the 5 patients experienced a DLT in the 6-week period. The IRB has approved enrollment onto the triplet cohort.*

The dose escalation design, which has 3 planned dose levels, was based on the prior clinical experience with each of the 3 investigational agents with the intent to define the MTD for the combination treatment.

Dose levels cohorts	1	2	3
rhIL-15 (mcg/kg/day SC)	0.5	1	2
Nivolumab (mg; IV over 30 min)	240	240	240
Ipilimumab (mg/kg; IV over 90 min)	1	1	1
Number of patients	3 to 6	3 to 6	3 to 6

#### 5.1.2.1 Standard 3+3 Dose Escalation Phase

Three patients will be treated at each new dose level. Dose escalation will be based on DLTs observed during the first cycle of treatment. If none of the 3 patients develop DLT at the dose administered, escalation will continue in cohorts of 3 patients each. If a DLT during the first cycle is observed in any of the 3 patients, then the cohort will expand up to 6 patients. If a second DLT is observed during cycle 1, then up to a total of 6 patients will be enrolled to the next lower dose level cohort. If no more than 1 in 6 patients in a dose level have DLT during the first cycle, dose escalation is permitted. DLTs seen after the first cycle will not affect the dose escalation decisions.

Number of Patients with DLT at a Given Dose Level	Escalation Decision Rule
0 out of 3	Enter 3 patients at the next dose level.
$\geq 2$	Dose escalation will be stopped. This dose level will be declared the maximally administered dose (highest dose administered). Three (3) additional patients will be entered at the next lowest dose level if only 3 patients were treated previously at that dose.
1 out of 3	Enter at least 3 more patients at this dose level. 

• If 0 of these 3 patients experience DLT, proceed to the next dose level.

• If 1 or more of this group suffer DLT, then dose escalation is stopped, and this dose is declared the maximally administered dose. Three (3) additional patients will be entered at the next lowest dose level if only 3 patients were treated previously at that dose.

$\leq 1$ out of 6 at highest dose level below the maximally administered dose	This is generally the recommended phase 2 dose. At least 6 patients must be entered at the recommended phase 2 dose.
---	--

The MTD will be based on the assessment of DLTs, and will be defined as the dose level at which less than one-third of patients (0/3 or 0-1/6 patients) treated experience a DLT, with the next higher dose level demonstrating a one-third or greater number of patients ( $\geq 2$  patients) having DLT. A DLT is defined as an AE that is felt to be related (possibly, probably, or definitely) to administration of study drugs, and meets prespecified criteria (see [Section 5.2](#)). If a subject did not experience DLT and did not finish 1 cycle of treatment (42 days), he or she will not be evaluable for determination of the MTD and will be replaced in the dose level.

Patients will be encouraged to report any and all adverse events, given the high likelihood of toxicities with the triplet combination therapy. Monitoring of AEs will continue during subsequent cycles to determine the safety and feasibility of the treatment regimen over time and to discern whether there is any need to make changes to the protocol or informed consent.

rhIL-15 administration will be limited to the first 4 cycles of treatment. After completing 4 cycles, patients in the triplet cohort may continue on nivolumab and ipilimumab combination therapy for cycles 5 and onwards; they may not continue receiving rhIL-15. If there are concerns about toxicity during cycles 5 and onwards, patients may discontinue ipilimumab and continue receiving nivolumab monotherapy.

#### 5.1.2.2 Expansion Cohort

An expansion cohort of 15 patients will be treated at the MTD or the maximum administered dose. With 15 patients and a biopsy QA failure rate of 50% with respect to paired biopsies, there is an 85% likelihood of having at least 6 usable samples and a 95% likelihood of having at least 5 usable samples.

Dose levels cohorts	Expansion cohort
rhIL-15 (mcg/kg/day)	MTD
Nivolumab (mg)	240
Ipilimumab (mg/kg)	1
Number of patients	15

## 5.2 Definition of Dose-Limiting Toxicity

Dose escalation will be based on DLTs observed during the first cycle of treatment.

**5.2.1** Grade  $\geq 3$  non-hematologic toxicity will be considered dose limiting, with the following exceptions:

- 5.2.1.1 Grade 3 fatigue lasting  $\leq 7$  days.
- 5.2.1.2 Grade 3 diarrhea will only be considered dose limiting if it is caused by colitis or, if after 72 hours, it is refractory to treatment. Grade 4 diarrhea will be dose limiting.
- 5.2.1.3 Grade 3 nausea and vomiting will only be considered dose limiting if after 72 hours it is refractory to maximal anti-emetic therapy and unable to be corrected to Grade  $\leq 2$  or baseline.
- 5.2.1.4 Grade 3 rise in creatinine, not corrected to Grade 1 or baseline after intravenous fluids within 24 hours, will be considered dose limiting. All Grade 4 rises in creatinine will be dose limiting.
- 5.2.1.5 Grade 3 electrolyte toxicities unable to be corrected to Grade 2 or baseline within 24 hours will be considered dose limiting.
- 5.2.1.6 Grade 3 liver function test (ALT, AST, alkaline phosphatase, total bilirubin) abnormalities in the absence of clinical signs of hepatic dysfunction (lethargy, confusion, anorexia, pruritus, tremor) that persist  $\leq 3$  days will not be considered dose-limiting.

**5.2.2** Grade 4 hematological toxicity

- 5.2.2.1 Neutropenia: Grade 4 neutropenia of any duration accompanied by fever or infection will be considered dose limiting. Grade 4 neutropenia for  $>5$  days without fever or infection will be considered dose limiting. Transient neutropenia ( $\leq 5$  days) without fever or infection will not be considered dose-limiting. Twice weekly blood draws will be needed (after onset of grade 4 neutropenia) to monitor duration of neutropenia for the first 2 cycles. On subsequent cycles (cycle 3 and beyond), weekly blood draws will be monitored after onset of grade 4 neutropenia.
- 5.2.2.2 Thrombocytopenia: Grade 4 thrombocytopenia will be considered dose limiting. Grade 3 thrombocytopenia associated with bleeding will be considered dose limiting.
- 5.2.2.3 Anemia: Grade 4 anemia will be considered dose limiting.

**5.2.3** Any neurotoxicity Grade  $\geq 2$  that is not reversible to a Grade  $\leq 1$  within 2 weeks will be considered dose limiting.

5.2.3.1 Any adverse event requiring steroid treatment, with the exception of short-term use ( $\leq 2$  weeks) for skin rash or mucositis or use for endocrine replacement, will be considered dose limiting. Any adverse event requiring permanent discontinuation of study drugs will be considered dose limiting.

Any unexpected grade 4 or grade 5 adverse event considered to be at least possibly related to study drug will cause the protocol to be halted and the study design and informed consent reevaluated with the sponsor.

Management and dose modifications associated with the above adverse events are outlined in [Section 6](#).

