## **6.1 Dose Delay Criteria**

For toxicities that are not defined as DLT, next drug doses can be delayed for up to +3 days to allow for toxicities to resolve. Patients who meet criteria to resume treatment, the dosing days of nivolumab and ipilimumab may be adjusted within a +3 day window, as long as consecutive nivolumab doses are given at least 12 days apart. Patients who do not meet the criteria to resume treatment will be managed as specified in the dose delay and adverse event management tables below.

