### **rhIL-15 Dose Delays**

Patients should be monitored specifically for rhIL-15-associated toxicities that overlap with nivolumab and ipilimumab toxicity. These events include hypotension, hypoxia, rapid changes in peripheral blood lymphocytes, LFT elevation, and skin and organ infiltrates.

If a patient requires steroid treatment to manage toxicities, rhIL-15 should be held until the patient is tapered off steroids. IL-15 will be held for neutropenia grade 2 or higher (continuing other study drugs) if the patient is receiving benefit at the discretion of the PI in consultation with the medical monitor.

Neutropenia	Management/Next Dose for rhIL-15
≤ Grade 1	No change in dose
Grade 2 *	Hold until ≤ Grade 1. Resume at same dose level.
Grade 3 *	Hold* until < Grade 2.
Grade 4	Off protocol therapy

\* For neutropenia that does not improve to grade 1 within a 2-week time frame to resume re-treatment patients may be considered for dose-reduction of IL-15 or discontinuation at the discretion of the PI and in consultation with the medical monitor.

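### Brief afebrile grade 4 neutropenia in cycle 1 can count as no DLT, as a DLT, or as unevaluable, because Sections 5.2 and 6.1 do not say which rule prevails

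*Combined protocol and SAP*

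**What the plan says.** **Neutropenia.** Section 5.2.2.1 says that grade 4 neutropenia lasting 5 days or less "without fever or infection will not be considered dose-limiting". It provides the means to time the episode: "Twice weekly blood draws will be needed (after onset of grade 4 neutropenia) to monitor duration of neutropenia for the first 2 cycles". In Section 6.1, the grade 4 row of the rhIL-15 neutropenia table reads "Off protocol therapy". The neutropenia table for ipilimumab and the nivolumab/ipilimumab combination has the same entry. Neither row has a duration condition, whereas the grade 2 and 3 rows in both tables call for a hold.

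**Catch-all.** Section 5.2.3.1 adds two triggers. One is permanent discontinuation: "Any adverse event requiring permanent discontinuation of study drugs will be considered dose limiting". The other is steroid use: "Any adverse event requiring steroid treatment, with the exception of short-term use" in rash or mucositis, or endocrine replacement. The text then refers to Section 6 for management of the same events.

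**Liver tests.** Section 5.2.1.6 exempts grade 3 "abnormalities in the absence of clinical signs of hepatic dysfunction" that last 3 days or less. The liver table in Section 6.1 says, for grade 3 AST, ALT or bilirubin, to discontinue the checkpoint inhibitor(s) and start steroids. It sets no condition on duration or symptoms.

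**Escalation and evaluability.** Section 5.1.2.1 bases escalation on cycle-1 DLTs. Sections 5.1.2.1 and 13.1 both replace, as unevaluable for the MTD, a patient who has no DLT and does not complete the 42-day cycle. Section 13.1 restates the catch-all in other words: it refers to loss of a single agent, and to long-term corticosteroids only.

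**The concern.** Section 5.2.2.1 looks deliberate. Section 2.1.4 reports transient grade 3/4 neutropenia with rhIL-15 and attributes it to redistribution of neutrophils rather than depletion. Followed literally, Section 6.1 and then 5.2.3.1 undo that exemption, because a patient taken off protocol therapy has permanently stopped study drugs. If the exemption is instead held to prevail but Section 6.1 still ends treatment before day 42, the replacement rule applies, and a toxicity that ended treatment drops out of the escalation count.

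DLTs and the MTD are part of the primary objective, and the 3+3 rule acts on single patients. At 0/3 the dose escalates and at 1/3 the cohort expands; at 1/6 it escalates and at 2/6 it stops. With no written precedence, the classification would be made after the event is known, by people who can see which decision follows.

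**Working it through.** **Step 1: trace one event through the text.** Take a patient with 4 days of afebrile grade 4 neutropenia in cycle 1.

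- Section 5.2.2.1: not a DLT.
- Section 6.1, either neutropenia table: off protocol therapy.
- Section 5.2.3.1: permanent discontinuation, so a DLT.
- Sections 5.1.2.1 and 13.1: if not a DLT but off before day 42, unevaluable and replaced.

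The conflict does not depend on whether study drugs means one agent or all of them, since all protocol therapy stops.

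**Step 2: reproduce the plan's escalation table.** With true DLT rate p, a dose level escalates on 0/3, or on 1/3 followed by 0/3:

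P(escalate) = (1−p)³ + 3p(1−p)²·(1−p)³ = (1−p)³ + 3p(1−p)⁵.

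For p = 10% to 60% in steps of 10 points this gives 0.906, 0.709, 0.494, 0.309, 0.172 and 0.082. Section 13.1 prints .91, .71, .49, .31, .17 and .08. The table is correct and is not in dispute.

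**Step 3: apply the three readings.** Let p be the rate of other DLTs. Let q be the proportion of patients without another DLT who have the exempted event. The documents give no value for q; it is assumed here and taken to be independent of other DLTs.

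- A, not a DLT and evaluable: rate p.
- B, a DLT through 5.2.3.1: rate 1 − (1−p)(1−q).
- C, not a DLT, off therapy before day 42 and replaced: rate among evaluable patients p / [p + (1−p)(1−q)].

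With p = q = 0.10:

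- A: 0.9³ + 3(0.10)(0.9⁵) = 0.729 + 0.177 = 0.906.
- B: rate 1 − 0.9 × 0.9 = 0.19; 0.81³ + 3(0.19)(0.81⁵) = 0.531 + 0.199 = 0.730.
- C: rate 0.10/0.91 = 0.110; P(escalate) = 0.889.

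| p | q (assumed) | A | B | C |
|---|---|---|---|---|
| 10% | 5% | 0.906 | 0.824 | 0.898 |
| 10% | 10% | 0.906 | 0.730 | 0.889 |
| 10% | 20% | 0.906 | 0.536 | 0.868 |
| 20% | 5% | 0.709 | 0.622 | 0.691 |
| 20% | 10% | 0.709 | 0.536 | 0.671 |
| 20% | 20% | 0.709 | 0.378 | 0.626 |
| 30% | 5% | 0.494 | 0.425 | 0.472 |
| 30% | 10% | 0.494 | 0.360 | 0.449 |
| 30% | 20% | 0.494 | 0.248 | 0.399 |

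Every DLT under A is also a DLT under B, so A minus B is the probability that the two readings give different decisions at one dose level. At p = 10% it is 0.906 − 0.730 = 0.176 for q = 10%. For q = 2% the rate under B is 0.118 and the difference is 0.906 − 0.875 = 0.031.

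**The case against.** **The exemption is specific and should override the general clause.** That is a reasonable way to read 5.2.2.1, which is worded as a freestanding exclusion. But 5.2.3.1 covers any adverse event, comes later, makes no exception for it, and refers to the Section 6 tables. A second reader could fairly go the other way.

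**Section 6.1 has flexibility.** It says "IL-15 will be held for neutropenia grade 2 or higher (continuing other study drugs) if the patient is receiving benefit", at the investigator's discretion with the medical monitor. This can keep some grade 4 patients on treatment, and the objection stands to that extent. It makes the classification depend on a case-by-case judgement of benefit during cycle 1. The first restaging scan falls at about week 6, although the protocol does not say that benefit must be radiographic. Section 6.1 also says "For toxicities that are not defined as DLT, next drug doses can be delayed for up to +3 days", but that presupposes the DLT answer.

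**The weekly team review in Section 12.1 can settle cases, and the strict reading errs towards safety.** Both are true. Neither supplies a rule fixed in advance.

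**Stronger readings that a reader might infer.**

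- *That the liver rules contradict each other just as firmly.* They do not. Section 5.2.1.6 is an exception to the grade rule in 5.2.1 only. The liver table's grade 3 row says to discontinue, without adding permanently. Appendix C lets a patient started on steroids, but found not to need them for an autoimmune event, resume after two weeks, so starting steroids is not the same as requiring them. The transient rises in Section 2.1.4 were seen with continuously infused rhIL-15, whereas the liver table governs checkpoint-inhibitor events. What remains is conditional: a brief rise managed under that table triggers steroids at once, and 5.2.3.1 counts events that require steroids.
- *That study drugs is undefined.* Section 13.1 does indicate a single agent. The fair criticism is that the two sections differ, on agents and on steroids. Section 13.1's list is not exclusive, and 5.1.2.1 already points to 5.2.
- *That the high-grade liver rate in Table 3 gives a usable q.* It comes from ipilimumab at 10 mg/kg, and median resolution of grade 2 to 4 liver events was 4.0 weeks. Events lasting that long exceed the 3-day exemption and are mostly DLTs under any reading.

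**Conclusion.** The neutropenia conflict is in the current text and needs resolving before the DLT count can be called prespecified. One event has three possible classifications, and a single patient can change the dose decision.

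The size of the effect is unknown. The documents give no rate for brief afebrile grade 4 neutropenia with subcutaneous rhIL-15 in the triplet, and the rhIL-15 adverse event list in Section 7.1.3 gives no frequencies. The 0.91, 0.73 and 0.89 are an illustration that rests on p = q = 10%, on independence, and, for the last figure, on every exempt patient coming off before day 42 and being replaced. If q is about 2%, the gap between the non-DLT and DLT readings is only about 0.03.

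The liver issue is weaker and conditional, and the 5.2.3.1/13.1 difference is one of wording. Nothing in the documents shows that any escalation decision already taken was wrong.

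**What to change.** 1. State in 5.2.3.1 which rule prevails for events exempted by 5.2.2.1 and 5.2.1.6. There are two coherent choices.
   - *Lenient:* such an event is not a DLT even if Section 6 stops a drug or starts steroids, and the patient stays evaluable as a non-DLT and is not replaced. Without the evaluability clause, the event would drop out of the count.
   - *Strict:* such an event is a DLT whenever therapy is permanently stopped, and the exemption wording is narrowed to match.
2. Use one wording for the agents and one steroid rule in 5.2.3.1 and 13.1.
3. For patients already treated, tabulate DLTs and evaluability by dose level under each reading. If the tables agree, the question is closed for those patients.

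Section 6 can stay as it is: its hepatic guidance recommends early treatment, and only the counting rule is missing.

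The cost is a short wording amendment, sponsor and clinical agreement on the direction, and one extra table. The lenient choice allows escalation although a patient came off therapy for a brief event. The strict choice may stop escalation on transient laboratory changes.

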### 5.3 General Concomitant Medication and Supportive Care Guidelines

Because there is a potential for interaction of the study agents with other concomitantly administered drugs, the case report form must capture the concurrent use of all other drugs, over-the-counter medications, or alternative therapies. The Principal Investigator should be alerted if the patient is taking any agent known to affect or with the potential for drug interactions. The study team should check a frequently-updated medical reference for a list of drugs to avoid or minimize use of. A Patient Drug Information Handout/Wallet Card is provided ([Appendix B](#)).

#### Drugs to be avoided:

- Traditional herbal or homeopathic or natural medicines. Ingredients for such medicines have not been fully studied, and their use may result in unanticipated drug-drug interactions that may cause or confound assessment of toxicity.
- Immunostimulatory agents, including but not limited to interferon (IFN)- $\alpha$ , IFN- $\gamma$ , anti-TNF- $\alpha$ , or IL-2 (aldesleukin) (prohibited during the study and for 10 weeks after the last dose of study drugs). These agents, in combination with the study drugs, could potentially increase the risk for autoimmune conditions.
- Immunosuppressive medications, including but not limited to cyclophosphamide, azathioprine, methotrexate, and thalidomide. These agents could potentially alter the activity and the safety of study drugs. However, systemic corticosteroids and other immunosuppressants may be indicated after starting the study drugs to treat immune-related adverse reactions.
- Live vaccines and live, attenuated vaccines (prohibited for 30 days prior to study agents, during the study, and for 100 days after the last dose of study drug). Inactivated vaccines are permitted.
- Initiation of granulocyte colony-stimulating factors (e.g., innovator and biosimilar forms of filgrastim, sargramostim, and/or pegfilgrastim) should be discussed with the Medical Monitor.

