Grade 2	
Hold dose pending evaluation. Resume no change in dose after pulmonary and/or ID consultation excludes ipilimumab and associated lymphocytic pneumonitis. Off nivolumab/Ipilimumab if steroids are required.
	
For Grade 2 (mild to moderate new symptoms)
 
 
- Monitor symptoms daily and consider hospitalization
 
- Promptly start systemic steroids (e.g. prednisone 1-2 mg/kg/day or IV equivalent)
 
- Reimaging as clinically indicated
 
- If no improvement within 3-5 days, additional workup should be considered and prompt treatment with IV methylprednisolone 2-4 mg/kg/day to be started
 
- If still no improvement within 3-5 days despite IV methylprednisolone at 2-4 mg/kg/day, promptly start immunosuppressive therapy such as TNF inhibitors (e.g. infliximab at 5 mg/kg every 2 weeks).
 
 
Caution: rule out sepsis and refer to infliximab label for general guidance before using infliximab

Grade 3	
Hold dose pending evaluation. Resume no change in dose after pulmonary and/or ID consultation excludes ipilimumab and associated lymphocytic pneumonitis. Off nivolumab/Ipilimumab if steroids are required.
	
For Grade 3 or 4 (severe or new symptoms, new/worsening hypoxia, life threatening):
 
 
- Promptly initiate empiric IV methylprednisolone 1-4 mg/kg/day or equivalent
 
- Obtain pulmonary and infectious disease consult
 
- Hospitalize the subject
 
- Supportive care (oxygen etc.)
 
- If no improvement within 3-5 days, additional workup should be considered and prompt treatment with additional immunosuppressive therapy such as TNF inhibitors (e.g. infliximab at 5 mg/kg every 2 weeks) to be started.
 
 
Caution: rule out sepsis and refer to infliximab label for general guidance before using infliximab

Pneumonitis	Management/Next Dose for Nivolumab and Combination Nivolumab/ipilimumab	Toxicity management
		
using infliximab
 
 
- Once improving, gradually taper steroids over <math>\geq 28</math> days and consider prophylactic antibiotics, antifungals and in particular, anti-PCP treatment (please refer to current NCCN guidelines for treatment of cancer-related infections)
 

Grade 4	Off nivolumab/ipilimumab treatment.	See above

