All Grades	
Distinguishing inflammatory pneumonitis is often a diagnosis of exclusion for patients who do not respond to antibiotics and have no causal organism identified including influenza. Most patients with respiratory failure or hypoxia will be treated with steroids. Patients who require steroids should be taken off nivolumab treatment. Bronchoscopy may be required and analysis of lavage fluid for lymphocytic predominance may be helpful. Patients with new lung nodules should be evaluated for sarcoid like granuloma.
 
The investigator is requested to differentiate between non-infectious pneumonitis, and infectious pneumonitis (viral, bacterial, or fungal), aspiration pneumonitis, or other pneumonitis clearly not due to a potential hypersensitivity reaction to the study agent infusions; and provide the basis for his/her assessment that it is infectious or other, as appropriate. The investigator is requested to report with the most specific clinical terms to describe the condition, not simple “pneumonitis”.
	

Additional guidance can be found in the Pulmonary Adverse Event Management Algorithm ([Appendix C](#)). Consider recommending seasonal influenza killed vaccine for all patients.

Fatigue	Management/Next Dose for Nivolumab and Combination Nivolumab/ipilimumab
$\leq$ Grade 1	Continue therapy. No change in dose.
Grade 2	Continue therapy. No change in dose.
Grade 3	Hold until $\leq$ Grade 2. Resume at same dose level.
Grade 4	Off nivolumab/ipilimumab therapy.

Fatigue is the most common adverse event associated with immune checkpoint therapy. Grade 2 or greater fatigue should be evaluated for associated or underlying organ involvement including pituitary, thyroid, and hepatic, or muscle (CPK) inflammation.

Neurologic events	Management/Next Dose for Nivolumab and Combination Nivolumab/ipilimumab
$\leq$ Grade 1	Hold dose pending evaluation and observation. Resume with no change in dose when resolved to baseline.
Grade 2	Hold dose pending evaluation and observation. Hold until baseline. Off protocol treatment if steroids are required. Resume at same dose level

Neurologic events	Management/Next Dose for Nivolumab and Combination Nivolumab/ipilimumab
	for peripheral isolated n. VII (Bell's palsy).
Grade 3	Off nivolumab/ipilimumab treatment.
Grade 4	Off nivolumab/ipilimumab treatment.
Patients who require steroids should be taken off nivolumab/ipilimumab treatment.	

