### Cardiac Toxicities Nivolumab and combination of nivolumab/ipilimumab

- Drug will be held for any indication suggestion of cardiac dysfunction of any grade pending evaluation.
- For patients with evidence of CHF, MI, cardiomyopathy, or myositis cardiac evaluation including lab tests and cardiology consultations as clinically indicated including EKG,

CPK, troponin, ECHO cardiogram. Drug will be held for grade 2 cardiac dysfunction pending evaluation.

- Drug will be permanently discontinued for grade 3 or 4 cardiac dysfunction and grade 2 events that do not recover to baseline or that reoccur.
- Treatment as clinically indicated for cardiomyopathy.

Cardiac 	Management/Next Dose for Nivolumab and Combination Nivolumab/ipilimumab
≤ Grade 1	Hold dose pending evaluation and observation.  Evaluate for signs and symptoms of CHF, ischemia, arrhythmia or myositis.  Obtain history EKG, CK (for concomitant myositis), CK-MB. Repeat troponin, CK and EKG 2-3 days. If troponin and labs normalize, may resume therapy. If labs worsen or symptoms develop, then treat as below.
Grade >2 with suspected myocarditis	Hold dose.  Admit to hospital. Cardiology consult. Rule out MI and other causes of cardiac disease. Cardiac Monitoring. Cardiac Echo. Consider cardiac MRI and cardiac biopsy. Initiate high dose methylprednisolone. If no improvement within 24 hours, add either infliximab, ATG or tacrolimus. Resume therapy if there is a return to baseline and myocarditis is excluded or considered unlikely.
Grade >2 with confirmed myocarditis	Off protocol therapy. Admit to CCU (consider transfer to nearest Cardiac Transplant Unit). Treat as above. Consider high dose methylprednisolone. Add ATG or tacrolimus if no improvement.

Including CHF, LV systolic dysfunction, myocarditis, CPK, and troponin.

Patients with evidence of myositis without myocarditis may be treated according to “all other events”.

Unexplained atrial arrhythmias, new onset atrial fibrillation, conduction abnormalities, and focal cardiomyopathy (Takasubo) may be associated with myocarditis even with normal echocardiograms. These events may require evaluation with a cardiac MRI to confirm myocarditis when clinically indicated.

Myositis may occur with myocarditis and/or Guillain Barre syndrome.

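### Section 5.3 lists anti-TNF-alpha as immunostimulatory and bans it by name, while Section 6.1 gives infliximab as a rescue drug; the intent can be inferred, but no visible text expressly lifts the ban

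*Combined protocol and SAP*

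**What the plan says.** Under the list of drugs to be avoided, Section 5.3 has a bullet on immune stimulants that names IFN-alpha, IFN-gamma, anti-TNF-alpha and IL-2. These are "prohibited during the study and for 10 weeks after the last dose of study drugs", and the reason given is: "These agents, in combination with the study drugs, could potentially increase the risk for autoimmune conditions". The bullet has no exception.

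The next bullet covers immunosuppressive drugs and names cyclophosphamide, azathioprine, methotrexate and thalidomide. It does have an exception: "However, systemic corticosteroids and other immunosuppressants may be indicated after starting the study drugs to treat immune-related adverse reactions". It does not mention anti-TNF agents.

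Section 6.1 takes the opposite view of the class:

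- **Grade 2 pneumonitis**, still not improving after escalation to IV methylprednisolone: "promptly start immunosuppressive therapy such as TNF inhibitors (e.g. infliximab at 5 mg/kg every 2 weeks".
- **Grade 3 or 4 pneumonitis**, not improving in 3-5 days: "prompt treatment with additional immunosuppressive therapy such as TNF inhibitors", with the same infliximab dose as the example.
- **Both pneumonitis rows** carry a caution: "rule out sepsis and refer to infliximab label for general guidance before using infliximab".
- **Suspected myocarditis**, after high-dose methylprednisolone: "If no improvement within 24 hours, add either infliximab, ATG or tacrolimus".

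In Appendix C, the text with the GI algorithm rules infliximab out only in perforation or sepsis, which presumes that it may be used otherwise.

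**The concern.** One drug class carries two opposite labels and two opposite instructions. The reason given for the ban, more autoimmunity, is the reverse of the purpose for which Section 6.1 uses the drug.

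What is at stake is patient safety and trial conduct. A pharmacist or covering clinician who checks the prohibited list before dispensing would find the class barred by name, at a point where Section 6.1 asks for prompt action or sets a 24-hour limit. A site that follows Section 6.1 with infliximab has, on a literal reading, departed from Section 5.3, and Section 12.1 requires protocol deviations to be reported at once to the IRB and the sponsor. Immune toxicity is expected here: Section 5 anticipates a high likelihood of toxicity with the triplet.

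**Working it through.** No sample size, power or event count enters this point, so the check is a comparison of the texts plus one timing check.

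**1. Classification.** Section 5.3 treats anti-TNF-alpha as an immune stimulant. The Section 6.1 pneumonitis table treats TNF inhibitors as immunosuppressive therapy. Both labels cannot be right. The other agents named in the 5.3 bullet are all cytokines, and the autoimmunity rationale fits them. Anti-TNF-alpha is the item out of place.

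**2. Instruction.** One bullet bars the class by name. Section 6.1 offers it in three places: Grade 2 pneumonitis, Grade 3-4 pneumonitis and suspected myocarditis (2 + 1 = 3). The GI caution in Appendix C presumes use but does not instruct it, so it is supporting evidence and not a fourth place.

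**3. Does stopping the antibodies avoid the ban?** Section 6.1 takes a pneumonitis patient off nivolumab and ipilimumab if steroids are needed. The ban continues for 10 × 7 = 70 days after the last dose. Time from the start of steroids to rescue in Section 6.1:

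- Grade 2 pneumonitis: two successive steps of 3-5 days, so 3 + 3 = 6 to 5 + 5 = 10 days.
- Grade 3-4 pneumonitis: 3 to 5 days.
- Suspected myocarditis: 24 hours.

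These intervals are short against 70 days, so stopping treatment does not by itself move the rescue outside the prohibited period.

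**4. Does any text settle precedence?** Section 5.2.3.1 refers management of adverse events to Section 6, and Section 6.2 refers specific events to Appendix C. Both suggest that Section 6 should guide treatment. Neither mentions the 5.3 ban or says that it yields. The exception for other immunosuppressants comes closest, but it belongs to a bullet that, by the protocol's own sorting, does not contain anti-TNF-alpha.

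**5. Effect on the primary endpoint.** Under Section 5.2.3.1, an adverse event that needs steroids is dose limiting, except for short courses for rash or mucositis and endocrine replacement. Related pneumonitis or myocarditis treated with steroids in cycle 1 therefore already counts before a TNF inhibitor is considered. The DLT count is the same whether or not infliximab follows.

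**The case against.** The best reply is that the protocol nearly resolves this itself. Section 5.3 allows other immunosuppressants for immune-related reactions, and Section 6.1 calls TNF inhibitors immunosuppressive. Read together, infliximab rescue is permitted. Section 5.3 is also headed as general guidance, whereas the pneumonitis table is specific: it gives drug, dose, interval, trigger and a label caution. A clinician treating refractory pneumonitis would be working from that table. On this view the entry is a drafting slip.

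Most of that stands, and it limits the point to a literal conflict. It does not remove the conflict, because the reader must first reject the protocol's own classification before the exception can apply to a drug banned by name.

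Three stronger readings are not supported:

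- **That the protocol blocks treatment of steroid-refractory toxicity.** The pneumonitis rows offer TNF inhibitors only as an example, and suspected myocarditis has ATG and tacrolimus as alternatives. Another immunosuppressant could satisfy both sections.
- **That infliximab is also given for confirmed myocarditis.** That row refers back to the one above, but the add-on drugs it names are ATG and tacrolimus only. It should not be counted.
- **That nothing anywhere resolves the matter.** For pneumonitis, Section 6.1 says: "Additional guidance can be found in the Pulmonary Adverse Event Management Algorithm". The pulmonary and GI figures in Appendix C are not visible in the copy reviewed, so a clarifying note there cannot be excluded.

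**Conclusion.** The point holds as a literal contradiction in an operative section: a drug class is misclassified and banned by name in Section 5.3, and offered as rescue in three places in Section 6.1, with no express override in the visible text. The intended reading is fairly clear, so this is a wording correction that should be made for safety and conduct. It is not a flaw in the design.

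A reader might infer that the MTD decision is at risk. It is not, because steroid-treated pneumonitis or myocarditis in cycle 1 is already dose limiting. No other statistical quantity depends on this point.

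No patient count is offered. Section 2.1 reports that 50 to 75% of patients on combined anti-PD-1 and anti-CTLA-4 regimens received corticosteroids or other remitting agents, but that is not a rate of steroid-refractory events or of TNF-inhibitor use, and the documents give neither. The conclusion rests on the visible text and assumes that the Appendix C figures contain no override.

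**What to change.** Delete anti-TNF-alpha from the immunostimulatory bullet in Section 5.3 and list it under immunosuppressive medications, where the existing exception for immune-related reactions would apply. Alternatively, leave it where it is and add that TNF inhibitors are permitted to treat immune-related adverse events as set out in Section 6.1 and Appendix C. The first option is cleaner because it also corrects the classification and the mismatched rationale. The sponsor's medical team should settle the wording and check it against the Appendix C figures.

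The cost is one line in a protocol amendment, with no change to sample size, procedures, dose-escalation rules or analysis.
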